4.10. Safety Evaluation

All safety summaries and analyses will be based on the Safety Set as defined in Section 4.5.

4.10.1. Extent of Exposure

Study drug will be administered as subcutaneous injections. A descriptive summary of exposure variables will be provided for patients who took ISIS 721744 80 mg:

- Amount of active Study Drug (ISIS 721744) (mg)
- Duration of active Study Drug (ISIS 721744) exposure (days) from the first dose date/time to the last dose date/time + pre-specified duration in days, or to the study termination date, which occurred earlier.
 - for cohort A, the pre-specified duration is 28 days
 - for cohort B, the pre-specified duration is 56 days

4.10.2. Adverse Events (AEs)

AEs will be coded using the MedDRA Version 26.1 or higher.

Treatment-emergent adverse events (TEAEs) will be tabulated and are defined as those AEs that either start or worsen in severity on or after the date/time of first dose of study treatment.

In addition, if severity of an AE changes during the study, a separate AE will be recorded for each severity on the AE CRF. "first" and "second" AE will be identify based on AE start date. AE start date of the second record is AE stop date of first record. AE severity (mild/moderate/severe) are compared between these 2 linked records in a pair for further defining TEAE. Consider 2 cases below:

- Case 1: The first AE record in the pair occurs before first dosing, and the second AE record occurs after first dosing.
 - If the AE severity of the second record is worse than that of the first record, then only the second AE is deemed as a TEAE. Otherwise, neither record is considered as TEAE.
- Case 2: Both AE records in the pair occur after first dosing.
 - If the AE severity on the second record is worse than the severity on the first record, then count both records as treatment-emergent. But, if the severity improves, then only count the first record as treatment-emergent.

All TEAEs identified based on the rules above will be summarized in the event number analysis.

TP-GDO-WW-016-08 CONFIDENTIAL Project Document Version No. 2.0 Effective Date: 26 Nov 19 Project Document Effective Date: 13 Dec 2023 Related to: SOP-GDO-WW-019 Page 39 of 61

The most conservative approach will be used to determine if the event occurs after the treatment. For example, if the onset date or resolution date of an AE is prior to the first study treatment date, it will be considered to have occurred prior to the study period. If the onset or resolution date of an AE is a partial date with only month or year available or complete missing, then the event is assumed to be within the study period unless the year is prior to the year of the first study treatment date, or if in the same year, the month is prior to the month of the first study treatment date.

The incidence of AEs will be summarized by MedDRA PT and SOC for:

- Any TEAEs
- Potentially Related TEAEs. Related is defined as "Related", "Possible", or missing relationship to Study Drug (ISIS 721744 or placebo)
- Any TEAEs by severity. At each level of patient summarization, a patient is classified according to the highest severity if the patient reported one or more events. AEs with missing severity will categorized as "Missing" for this summary
- Related TEAEs by severity
- Serious AEs (SAEs)
- Serious and related TEAEs

AE summaries will be ordered alphabetically for SOC, and PT within SOC and decreasing frequency for SOC, and PT within SOC, in the overall column.

A by-patient listing of all AEs (including non-treatment-emergent events) will be provided. AEs that lead to study discontinuation or investigational drug discontinuation will also be listed separately. Non-treatment emergent adverse event will be flagged in the data listing.

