3.4.3. Post-Treatment

Patients are to return to the Study Center for post-treatment follow-up visits (or Home Healthcare, if available), as arranged by the Study Center personnel, per the Schedule of Procedures in Appendix A. Alternatively, patients who complete Study Visit Week 25, and meet eligibility requirements, may enroll in the OLE study any time after the Week 25 visit. If a patient chooses to enroll in the OLE study, the patient will discontinue participation in the CS5 Post-Treatment Period prior to the first visit in the OLE study. Patients may be required to attend additional visits for monitoring of AEs or abnormal investigation results. The frequency of additional monitoring will be determined by the Sponsor Medical Monitor in consultation with the Investigator or designee.

The final study visit for patients not enrolling in the OLE will be the Week 13 Post-Treatment Period Visit.

Throughout the study including during the Post-Treatment Period, patients may be required to attend additional visits for monitoring of AEs or abnormal investigation results. The frequency of additional monitoring will be determined by the Sponsor Medical Monitor in consultation with the Investigator or designee.

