Patients who experience at least 5 attacks/month for 2 consecutive months after Week 5 will have the opportunity to terminate from the Treatment Period and either continue in the Post-Treatment Period or enter into an OLE. A decision to terminate a patient from the Treatment Period for this reason will be made by the Investigator or designee in consultation with the Sponsor Medical Monitor. Patients who complete Study Visit Week 25, and meet eligibility requirements, may enroll in an OLE study after the Week 25 visit. If a patient chooses to enroll in the OLE study, the patient will discontinue participation in ISIS 721744-CS5 prior to the first visit in the OLE study.

Patients who discontinue treatment will attend the ET Visit and will be encouraged to complete the Post-Treatment Period, unless consent/assent is withdrawn.

Detailed information regarding the study procedures is presented in Section 6 and Appendix A. Appendix B includes a list of laboratory analytes required for the study.

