9.4.2. Non-Serious Adverse Events

The recording of non-serious AEs will begin after the patient signs the ICF and will stop at the end of the patient's Post-Treatment Period, which is defined as completion of the Week 13 Visit of the Post-Treatment Period, or patient has Day 1/Week 1 in the OLE study. The Investigator or designee will monitor each patient closely and record all observed or volunteered AEs on the eCRF.

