- Patients will be instructed to report details of any HAE attack to the study site within 72 hours of the onset of the attack. The following details relating to each HAE attack will be collected: localization, severity, course of attack, required on-demand treatment(s), and the frequency and dose of on-demand treatment.

¹ Assessments and procedures may be conducted by a Home Healthcare professional (if available).

Weeks/days from end of treatment. End of treatment is defined as 1 dosing interval (i.e., 4 weeks/28 days for Cohort A and 8 weeks/56 days for Cohort B) post-last dose.

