2.3. Safety Objectives

To evaluate safety and tolerability of ISIS 721744 in patients with HAE.

2.4. **Exploratory Objectives**

To further characterize the effects of ISIS 721744 on health economic and utilization parameters and additional Patient Reported Outcomes (PROs) and biomarkers.

3. **INVESTIGATIONAL PLAN**

3.1. **Overall Study Design and Plan**

This study is a phase 3, randomized (ISIS 721744:placebo), double-blind, placebo-controlled trial conducted in multiple centers to evaluate the efficacy and safety of ISIS 721744 in preventing angioedema attacks in patients with HAE-1 (Type I) and HAE-2 (Type II).

Approximately 84 patients are planned to be enrolled in the study. Patients will be randomized in a 2:1 ratio to Cohort A (ISIS 721744 or placebo every 4 weeks) or Cohort B (ISIS 721744 or placebo every 8 weeks), respectively. Within each Cohort, patients will be randomized in a 3:1 ratio to receive 80 mg of ISIS 721744 or matching volume of placebo.

Detailed information regarding the study procedures is presented in the Study Protocol.

The study will consist of Screening, Treatment, and Post-Treatment Periods. Patients may be required to attend additional visits for monitoring of adverse events (AEs) or abnormal investigation results.

The length of each patient's participation in the study is approximately 11 months (or 12 months for UK), which includes an up to 56-day Screening Period, a 24-week Treatment Period, and an up to 13-week (or up to 17-week, in UK only) Post-Treatment Period, unless the patient chooses to enroll in the open-label extension (OLE) study.

Patients who experience at least 5 attacks/month for 2 consecutive months after Week 5 will have the opportunity to terminate from the Treatment Period and either continue in the Post-Treatment Period or enter into an OLE study. Patients who complete Study Visit Week 25, and meet eligibility requirements, may enroll in an OLE study after the Week 25 visit. If a patient chooses to enroll in the OLE study, the patient will discontinue participation in ISIS 721744-CS5 prior to the first visit in the OLE study.

Patients who discontinue treatment will attend the Early Termination Visit and will be strongly encouraged to complete the Post-Treatment Period, unless consent/assent is withdrawn.

TP-GDO-WW-016-08 **Project Document Version No. 2.0 CONFIDENTIAL** Effective Date: 26 Nov 19 **Project Document Effective Date**: 13 Dec 2023 Related to: SOP-GDO-WW-019 Page 11 of 61

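### TEAEs have no end date but AE recording stops at OLE entry, so the general AE percentages pool observation times of mostly 24 to 37 weeks with no time-adjusted rate

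*Combined protocol and SAP*

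**What the plan says.** **Start of the window.** SAP 4.10.2 counts as TEAEs all events "defined as those AEs that either start or worsen in severity on or after the date/time of first dose of study treatment". Neither that section nor any other gives an upper limit.

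**End of recording.** Protocol 9.4.2 ends non-serious AE recording at "completion of the Week 13 Visit of the Post-Treatment Period, or patient has Day 1/Week 1 in the OLE study". Protocol 9.4.1 uses the same stop for SAEs.

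**Length of the periods.** SAP 3.1 plans "a 24-week Treatment Period, and an up to 13-week (or up to 17-week, in UK only) Post-Treatment Period". Footnote 2 of protocol Appendix A counts post-treatment weeks from end of treatment: "End of treatment is defined as 1 dosing interval" after the last dose.

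**Routes into the OLE.** Under protocol 3.4.3, eligible Week 25 completers "may enroll in the OLE study any time after the Week 25 visit". Under protocol 6.1.2, patients with five or more attacks a month in two successive months once past Week 5 "will have the opportunity to terminate from the Treatment Period and either continue in the Post-Treatment Period or enter into an OLE".

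**Summary measure.** SAP 4.10.2 tabulates AE incidence by system organ class and preferred term. SAP 4.2.1 presents categorical data as counts and percentages. SAP 4.10 contains no person-time AE rate and no AE table restricted to treatment. That the percentages are crude is inferred from these three facts; the SAP does not use the word.

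**The concern.** Time under AE observation is set partly by a decision taken after randomisation: whether and when to enter the OLE. A patient watched longer has more chance of a first event at the same underlying rate. If arms differ in how many patients roll over, or how soon, the active-versus-placebo safety comparison in protocol 10.6.2 can move without any drug effect. Even with equal rollover, the percentages have no defined time frame and mix follow-up with treatment time.

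Other parts of the SAP do not repair this:

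- SAP 4.2.2 defines a treatment period (last dose + 28 days in Cohort A, + 56 days in Cohort B), but limits it to an unnamed summary, and 4.10.2 does not refer to it.
- SAP 4.10.1 describes exposure only for patients on active drug, and only to last dose + 28 or 56 days. No table would show how long placebo patients were observed for AEs.
- The attack models (4.9.2.1) and the optional model for ER visits and hospitalisation (4.13.7) both use a log-time offset. The AE tables have no counterpart.
- SAP 4.9.1.5 runs the analyses once all patients have reached or left before Week 25, and updates them at End of Study. With no AE cut-off, follow-up at the first analysis also depends on enrolment date.

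**Working it through.** **1. The plan's own durations.** Screening up to 8 weeks + 24 + 13 = 45 weeks, or 45/4 = 11.25 four-week months. For the UK, 8 + 24 + 17 = 49 weeks, or 12.25. These agree with the stated 11 and 12 months. Protocol 3.4 calls the treatment period 25 weeks, but Day 169 is 168 days, or 24 weeks, after Day 1, so 24 is used.

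**2. AE observation time from first dose.**

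| Patient | Arithmetic | Weeks |
|---|---|---|
| Early escape, earliest OLE entry | Day 29 + 56 = Day 85 | 12 |
| Rolls over at Week 25 | Day 169 | 24 |
| Full follow-up | 168 + 91 = 259 days | 37 |
| Full follow-up, UK | 168 + 119 = 287 days | 41 |

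Both cohorts reach end of treatment on Day 169 (A: 141 + 28; B: 113 + 56). The 12 weeks takes a month as 28 days and is the earliest rule-based OLE entry; withdrawal of consent can end observation sooner. SAP 3.2.1 paraphrases the escape rule without the Week 5 condition; the condition is used here as in protocol 6.1.2 and SAP 3.1. The UK figure assumes that AE recording runs to the extended Week 17 visit; the UK amendment is not among the documents.

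**3. Effect of the window on a percentage.** Assume a constant hazard: h = -ln(1 - p24)/168 and P(t) = 1 - exp(-h t). For p24 = 30%, P(259) = 1 - 0.7^(259/168) = 42.3%.

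| 24 weeks | 37 weeks | 41 weeks |
|---|---|---|
| 10% | 15.0% | 16.5% |
| 30% | 42.3% | 45.6% |
| 70% | 84.4% | 87.2% |

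**4. Possible shift between arms.** The documents give no rollover shares. Assume equal true rates, with 90% of one arm and 50% of the other leaving at Week 25 and the rest staying to 37 weeks:

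- 30% event: 0.9 × 30 + 0.1 × 42.3 = 31.2%, against 0.5 × 30 + 0.5 × 42.3 = 36.1%. Gap 4.9 points.
- 70% event: 0.9 × 70 + 0.1 × 84.4 = 71.4%, against 0.5 × 70 + 0.5 × 84.4 = 77.2%. Gap 5.8 points.

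With equal shares the gap is zero, so the range runs from 0 to about 5 or 6 points as the difference in shares goes from 0 to 40 percentage points. One of 21 placebo patients is 1/21 = 4.8 points.

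**5. How many could escape early.** The planned placebo rate is 13.26/6 = 2.21 attacks a month. Counts were simulated in five 28-day windows after Week 5, with the rule met by two successive windows of at least 5. The chance is 2% for pure Poisson counts and 12% to 15% with gamma heterogeneity between patients (assumed shape 2 to 1). That is about 0.4 to 3.2 of 21 placebo patients. At the planned every-4-weeks rate (1.38/6 = 0.23) it is about 0%. The plan assumes no rate for every 8 weeks; at the 1.02 per 4 weeks in the lay summary it is at most about 2%.

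**6. Size of the escape effect.** At 12 weeks a 30% event reads 1 - 0.7^0.5 = 16.3%, and a 70% event 1 - 0.3^0.5 = 45.2%. If 15% of placebo left at Day 85 rather than Week 25, the placebo figure would fall by 0.15 × (30 - 16.3) = 2.1 points or 0.15 × (70 - 45.2) = 3.7 points. This is on the high side: it takes the largest simulated share, and assumes that all who meet the rule choose the OLE and leave at the first opportunity.

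**The case against.** A reader might infer that the OLE choice is response-driven throughout, so that the AE comparison is biased in a known direction. The documents do not support that. Only the early escape has a response criterion, and it allows follow-up instead of the OLE. The wider 24 versus 37-week spread comes from an option open to every eligible Week 25 completer, exercised while patients and sites are still blinded. Placebo patients with attacks and active patients doing well both have reasons to enter. Nor does the one documented mechanism favour the drug: it shortens placebo observation and would make the drug look relatively worse. These points stand.

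The size is also modest. The 90% versus 50% contrast is an assumption. With 42 and 21 patients, the standard error of a difference at 30% is √(0.3 × 0.7 × (1/42 + 1/21)) = 12.2 points, so 4.9 points is about 0.4 standard errors. The AE tables are descriptive and carry no test. This limits the consequence, but sampling noise does not justify an undefined time frame.

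The scope is narrower than all safety data. Local cutaneous reactions (LCRIS) and flu-like reactions are largely tied to the injection day or the next, or to stopping drug, and are also reported per injection (SAP 4.10.3.1 and 4.10.3.2). Laboratory, vital-sign and ECG summaries by visit separate treatment from post-treatment windows (SAP 4.2.3). All of these are essentially unaffected.

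Finally, protocol 2.4 gives a half-life of about 4 to 5 weeks, so Day 169 is only about one half-life after the last Cohort A dose. Counting follow-up events as treatment-emergent is therefore a defensible, inclusive choice. This stands as a reason to keep the all-study table, not as a reason to have no other.

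**Conclusion.** The point holds for the general TEAE, related-TEAE, severity, SAE and bleeding tables. Their percentages pool observation times of about 24 to 37 weeks (41 in the UK, on the stated assumption), and of about 12 weeks or more for a few early escapers, without a person-time rate or any display of observation time in placebo patients.

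For one patient type against another the effect is material: 30% against 42.3% under a constant hazard. Between arms it is unknown. It is zero if rollover is similar and about 5 to 6 points, or about one placebo patient, under the assumed 90% versus 50% split. For Week 25 completers, a link between the OLE choice and arm or response is plausible but undocumented. Early escape is expected mainly on placebo and would understate placebo TEAEs by roughly 2 to 4 points at the high end. The weakness is worth correcting because the remedy is cheap; it is not evidence that the safety comparison is wrong.

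**What to change.** In SAP 4.10.2:

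1. Keep the all-study TEAE table and state its end: the Post-Treatment Week 13 visit (for the UK, confirm whether Week 17), OLE Day 1 or study exit, whichever comes first.
2. Add an on-treatment table for the general AE and bleeding summaries, using the treatment period already defined in SAP 4.2.2 (last dose + 28 days in Cohort A, + 56 days in Cohort B), truncated at OLE first dose or study exit. Every treatment completer then has the same 24.0-week window in both cohorts.
3. Tabulate post-treatment AEs separately.
4. Add exposure-adjusted incidence (patients with an event per patient-year at risk) for all arms including placebo, and summarise AE observation time by arm. Early escapers still have shorter windows under item 2, so the common window cannot replace this.

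No change is needed for the LCRIS and flu-like tables.

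The cost is SAP wording and a few extra tables from AE dates already collected. The downside is that the on-treatment table omits late events that may fall within residual exposure, which is why the all-study table stays.

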4.10.3. Deaths, and Other Serious or Significant Adverse Events

4.10.3.1. Local Cutaneous Reactions at the Injection Site

Local cutaneous reaction at injection site (LCRIS) is defined as (A) moderate or severe AEs with the PTs including Injection site erythema, Injection site swelling, Injection site pruritus, or Injection site pain that started on the day of injection, persisted for at least 2 days or ongoing; or (B) any AE at the Study Drug injection site, regardless of severity, that leads to discontinuation of study drug, where AE at the Study Drug injection site is the principal reason for discontinuation. LCRIS will be summarized using the MedDRA coding system, by PT and by treatment group. Patients with moderate, severe and any LCRIS will also be summarized. Discontinuations of Study Drug (ISIS 721744 or placebo) due to AE at the injection site will be summarized separately.

Percentage of injections leading to those events will be summarized by PT and overall using the descriptive statistics. Additionally, percentage of injections leading to events will be summarized by moderate, severe severity and overall discontinuation of study drug due to AE at injection site.

TP-GDO-WW-016-08 CONFIDENTIAL Project Document Version No. 2.0 Effective Date: 26 Nov 19 Project Document Effective Date: 13 Dec 2023 Related to: SOP-GDO-WW-019 Page 40 of 61

Percentage of injections leading to LCRIS will be calculated as follows for each patient: $(A/B) \times 100$, where A = number of injections with a LCRIS, and B = total number of injections. Doses that are split across multiple injections are counted as a single injection.

LCRIS will be provided in a subject data listing.

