2.3.4. Clinical Experience

ISIS 721744 has been evaluated in the clinical setting in a Phase 1 safety study (ISIS 721744-CS1) and Phase 2 study (ISIS 721744-CS2).

Phase 1: ISIS 721744 was studied in 32 healthy volunteers in a double-blind, multiple-dose, dose-escalation study. Of these, 24 subjects received multiple doses of ISIS 721744. The 32 subjects were randomized into 4 cohorts (6 subjects each) to receive once-every-4-week SC doses of ISIS 721744 20, 40, 60, or 80 mg, or placebo (8 subjects) for a total of 12 weeks (4 total doses). All subjects received all planned doses of Study Drug (ISIS 721744 or placebo). The duration of Study Drug exposure was 84 days for each subject.

No serious adverse events (SAEs) were reported in the ISIS 721744-CS1 study. There were no early discontinuations from Study Drug or the study, and all subjects in the ISIS 721744 and placebo arms completed all study procedures. Adverse events at the injection site (defined as

any preferred term containing "injection site") were the most commonly reported treatment-emergent adverse events (TEAEs) in the ISIS 721744 treatment arms; no injection site-related TEAEs were reported in the placebo arm. There were no flu-like reactions or events of local cutaneous reaction at injection site (LCRIS) reported; LCRIS events were defined as (A) moderate or severe injection site erythema, swelling, pruritus, pain, or tenderness that started on the day of injection and persisted for at least 2 days; or (B) any AE at the injection site, regardless of severity, that led to discontinuation of Study Drug, where AE at the injection site was the principal reason for discontinuation. No relationship between incidence of TEAEs and the dose administered was observed.

Thirteen (13) AEs related to study treatment were reported for 4 (16.7%) subjects in the ISIS 721744 arm, and for 1 subject (2 events; 12.5%) in the placebo arm. One (1) subject each in the ISIS 721744 and placebo arm reported AEs of ECG T wave inversion (preferred term) that were assessed as related. Nine (9) of the total 13 related events with ISIS 721744 concerned Injection site-related events and were reported by 1 subject in the 80 mg arm. Additional related events were Tinnitus (1 subject, 1 event in the 60 mg arm), Headache (1 subject, 1 event in the 60 mg arm), and Epistaxis (1 subject, 1 event in the 20 mg arm). All TEAEs related to study treatment were mild in severity, and none were serious.

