9.4.3.2. Severity

The severity of AEs and SAEs relating to laboratory tests will be graded based on criteria from the Toxicity Grading Scale for Healthy Adult and Adolescent Volunteers Enrolled in Preventive Vaccine Clinical Trials, Sept. 2007 (refer to Appendix D). Any AE not listed in Appendix D will be graded as follows:

- **Mild:** The event is easily tolerated by the patient and does not affect the patient's usual daily activities
- **Moderate:** The event causes the patient more discomfort and interrupts the patient's usual daily activities
- **Severe:** The event is incapacitating and causes considerable interference with the patient's usual daily activities

The severity of AEs and SAEs relating to AEs at the injection site will be graded based on criteria from the Toxicity Grading Scale for Healthy Adult and Adolescent Volunteers Enrolled in Preventive Vaccine Clinical Trials, Sept 2007 (refer to Appendix D).

If the event is an SAE, then all applicable seriousness criteria must be indicated (criteria listed in Section 9.3.3.

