Hypercalcemia	10.5 – 11.0 mg/dL	11.1 – 11.5 mg/dL	≥ 11.6 mg/dL
Hyperglycemia [†]	Fasting glucose value >ULN - 160 mg/dL; Fasting glucose value >ULN - 8.9 mmol/L	Fasting glucose value >160 - 250 mg/dL; Fasting glucose value >8.9 - 13.9 mmol/L	>250 mg/dL; >13.9 mmol/L; hospitalization indicated
Hyperkalemia	5.1 – 5.2 mmol/L	5.3 – 5.4 mmol/L	≥5.5 mmol/L
Hypernatremia	144 – 145 mmol/L	146 – 147 mmol/L	≥148 mmol/L
Hypoalbuminemia	2.8 – 3.1 g/dL	2.5 – 2.7 g/dL	< 2.5 g/dL
Hypocalcemia	8.0 – 8.4 mg/dL	7.5 – 7.9 mg/dL	< 7.5 mg/dL
Hypoglycemia	65 – 69 mg/dL	< 64 mg/dL	< 55 mg/dL AND requires assistance of another person to actively administer carbohydrates, glucagon, or take other corrective actions [‡]
Hypokalemia	3.5 – 3.6 mmol/L	3.3 – 3.4 mmol/L	< 3.3 mg/dL
Hypomagnesemia	1.3 – 1.5 mg/dL	1.1 – 1.2 mg/dL	< 1.1 mg/dL
Hyponatremia	132 – 134 mmol/L	130 – 131 mmol/L	<130 mg/dL
Hypophosphatemia	2.3 – 2.5 mg/dL	2.0 – 2.2 mg/dL	< 2.0 mg/dL
Hypoproteinemia	5.5 - 6.0 g/dL	5.0 - 5.4 g/dL	< 5.0 g/dL
Lipase increased	1.1 – 1.5 x ULN	>1.5 – 2.0 x ULN	> 2 x ULN
Serum amylase increased	1.1 – 1.5 x ULN	>1.5 – 2.0 x ULN	> 2 x ULN

Adverse Event	Mild	Moderate	Severe				
Urine							
Proteinuria	Trace	1+	≥ 2+				
Hematuria	1 - 10 cells per high power field	11 – 50 cells per high power field	> 50 cells per high power field				

^{*}Grading for this parameter is derived from the Division of AIDS (DAIDS) Table for Grading the Severity of Adult and Pediatric Adverse Events Version 2.0, Nov 2014

The following grading recommendations for adverse events (AEs) at the injection site are based upon the Toxicity Grading Scale for Healthy Adult and Adolescent Volunteers Enrolled in Preventive Vaccine Clinical Trials, Sept 2007.

Local Reaction to Injectable Product	Mild (Grade 1)	Moderate(Grade 2)	Severe (Grade 3)	Potentially Life Threatening (Grade 4)
Pain	Does not interfere with activity	Repeated use of non- narcotic pain reliever > 24 hours or interferes with activity	Any use of narcotic pain reliever or prevents daily activity	Emergency room (ER) visit or hospitalization
Tenderness	Mild discomfort to touch	Discomfort with movement	Significant discomfort at rest	ER visit or hospitalization
Erythema/Redness *	2.5 – 5 cm	5.1 – 10 cm	> 10 cm	Necrosis or exfoliative dermatitis
Induration/Swelling **	2.5 – 5 cm and does not interfere with activity	5.1 – 10 cm or interferes with activity	> 10 cm or prevents daily activity	Necrosis

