4.9.2. Primary Efficacy Variable

The primary endpoint is the time-normalized number of Investigator-confirmed HAE attacks (per every-4-week) from Week 1 to Week 25.

Hereditary Angioedema Attack (HAE Attack)

During the study, patients will be instructed to report details of any HAE attack to the study site within 72 hours of the onset of the attack. Throughout the Screening, Treatment, and Post-Treatment Periods, site personnel will contact the patient approximately weekly in order to inquire about any attack that may have occurred.

The presence of these symptoms, including symptoms in one or more predefined locations in the protocol will not automatically be considered an HAE attack unless such a diagnosis is confirmed by the Investigator.

An Investigator-confirmed HAE attack will be defined as an event with signs or symptoms consistent with an attack in at least 1 of the locations noted above. A discrete attack will be counted if there is at least 24-hour symptom-free period between attacks.

Unique Investigator-confirmed HAE Attacks

To be counted as a unique Investigator-confirmed attack distinct from the previous attack, there must be at least 24 hours between the stop date/ time of the first event and the start date/time of the next event, for the attacks to be considered distinct. If there is less than 24 hours between the stop date/time of the first event and the start date/time of the next event, the events will be combined and counted as one unique attack.

When 2 or more events are combined as one unique Investigator-confirmed attack for efficacy analysis, parameters of the derived unique attack with combined multiple events will be defined in a conservative way.

- Events: Investigator-confirmed attacks.
- Dates: The start date/time will be the earliest start date/time of those multiple events; and the end date/time will be the latest end date/time of those multiple events.
- The severity will be defined as the highest severity among those multiple events.

TP-GDO-WW-016-08 CONFIDENTIAL Project Document Version No. 2.0 Effective Date: 26 Nov 19 Project Document Effective Date: 13 Dec 2023 Related to: SOP-GDO-WW-019 Page 28 of 61

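### Applied as written, the LCRIS definition misses or under-grades an injection-site reaction that worsens after the injection day, because each severity is a separate AE record (minor)

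*Combined protocol and SAP*

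**What the plan says.** SAP 4.10.3.1 defines LCRIS in two limbs. Limb (A) takes AEs with listed preferred terms (erythema, swelling, pruritus, pain at the injection site) that are moderate or severe and that meet the onset and duration conditions: "Injection site pain that started on the day of injection, persisted for at least 2 days or ongoing". Limb (B) takes an injection-site AE of any severity if it is the main reason for stopping study drug. Results are tabulated by preferred term, by moderate, severe and any, and as a percentage of each patient's injections, (A/B) × 100.

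SAP 4.10.2 sets out how AEs are recorded: "if severity of an AE changes during the study, a separate AE will be recorded for each severity on the AE CRF". On dating it says: "AE start date of the second record is AE stop date of first record". The severities "are compared between these 2 linked records in a pair for further defining TEAE"; no other use of the link is given. Protocol 9.4.3.5 fits this scheme, since a change in severity is one of the listed outcomes of a non-serious AE.

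Protocol 2.3.4 gives essentially the same onset and duration test for Phase 1 ("that started on the day of injection and persisted for at least 2 days") and, like the SAP, has no rule for a reaction that changes grade.

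**The concern.** Limb (A) places three conditions on an AE: grade, injection-day onset and persistence. If a reaction becomes several AEs as its grade changes, no single AE may meet all three even though the reaction does. Mild redness on the injection day that is moderate for the next three days yields a mild record, which fails on grade, and a moderate record, which fails on onset. The reaction began on the injection day; only the record split moves the onset date.

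LCRIS is the SAP's dedicated injection-site tolerability summary, and Protocol 2.3.4 reports its absence in both Phase 1 and Phase 2. With few events expected, one or two uncounted reactions could decide whether the table shows any LCRIS, or any severe LCRIS.

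**Working it through.** The plan states no figure to reproduce, so the check applies the two sections together.

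**Rules used.** Day 0 is the injection day. Records split at each change of grade, and each record stops on the date the next one starts (SAP 4.10.2). A record meets limb (A) if its grade is at least moderate, its start is day 0, and it lasts at least 2 days or is ongoing (SAP 4.10.3.1). The comparison treats the linked records as one reaction: onset on day 0, at least 2 days at moderate or worse, severity equal to the maximum.

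| Course | Records | Limb (A) per record | Per reaction |
|---|---|---|---|
| Moderate throughout | mod 0–5 | moderate | moderate |
| Mild, moderate from day 1 | mild 0–1, mod 1–5 | not counted | moderate |
| Mild, severe from day 2 | mild 0–2, sev 2–5 | not counted | severe |
| Mild, moderate later on day 0 | mild 0–0, mod 0–5 | moderate | moderate |
| Moderate, severe from day 1 | mod 0–1, sev 1–5 | not counted (stop minus start) or moderate (inclusive days) | severe |
| Moderate, severe from day 2 | mod 0–2, sev 2–5 | moderate | severe |

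The first and fourth rows are controls: where the grade is reached on the injection day and then holds, the two derivations agree.

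**Enumeration.** Take all courses of 3 to 7 days in total, with onset on day 0, one worsening step on a later day, and at least 2 days at moderate or worse.

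- Mild to moderate: 1+2+3+4+5 = 15 courses; 0 count.
- Mild to severe: 15 courses; 0 count.
- Moderate to severe: 2+3+4+5+6 = 20 courses; 0 count as severe under limb (A). As moderate, 15 count if 2 days means stop minus start (the step is on day 2 or later: 1+2+3+4+5), and all 20 count if days are inclusive. The SAP does not say which applies.

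These zeros follow from the definitions. They show which courses are affected, not how often they occur.

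**Illustration of size, on assumed inputs.** Suppose n patients each have one qualifying reaction, independently, and a share w of such reactions are mild on day 0, worsen later and do not stop treatment. The expected LCRIS count is n(1−w), and the chance that the table shows none is w^n.

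| | w = 10% | w = 25% | w = 50% |
|---|---|---|---|
| n = 1, chance of none | 10% | 25% | 50% |
| n = 2, chance of none | 1% | 6% | 25% |
| n = 3, chance of none | 0.1% | 1.6% | 12.5% |
| n = 3 of 42 (true 7.1%), expected rate 3(1−w)/42 | 6.4% | 5.4% | 3.6% |

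The 42 is the planned every-4-weeks group (SAP 4.15). Neither n nor w is in the documents.

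**The case against.** The strongest reply is that SAP 4.10.3.1 never says LCRIS is tested on unlinked records. SAP 4.10.2 describes the records as a linked pair, so the links exist and a programmer could join them. That is true, but the plan does not ask for it, and two programmers could report different counts from the same data.

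It can also be said that little is lost. When severity worsens after first dosing, both records are TEAEs; the severity table classifies each patient at the highest grade; all AEs are listed; and discontinuations for injection-site AEs are summarised separately. The LCRIS table is descriptive. All of this stands, and it keeps the point minor.

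Four stronger readings are tempting, and the documents do not support them.

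- A reader might infer that a reaction turning severe after the injection day can never be a severe LCRIS. Limb (B) admits it if it is the main reason for stopping drug, and worsening that falls on a later injection day could also qualify.
- A reader might infer that the pain scale builds the conflict in, since one route to Moderate takes more than a day. Protocol 9.4.3.2 does apply that scale ("The severity of AEs and SAEs relating to AEs at the injection site will be graded based on criteria from the Toxicity Grading Scale"), but the Appendix D criterion is "Repeated use of non- narcotic pain reliever > 24 hours or interferes with activity". Interference can occur on day 0, and nothing requires a Mild record first: pain with day-0 onset can be graded Moderate as one AE once its course is known.
- A reader might infer that every LCRIS figure is biased downwards. The moderate count is not: courses that go from moderate to severe stay in it when their maximum grade is severe.
- A reader might infer that the loss falls on the active arms. The lay summary shows injection-site reactions in 9/45, 1/23 and 0/22, which makes this plausible, but Protocol 2.5.1 calls Phase 2 injection-site AEs balanced, and neither source gives changes of severity.

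Finally, the SAP's rule for combining HAE attacks ("The severity will be defined as the highest severity among those multiple events") merges events less than 24 hours apart, which is a different problem. It shows only that such a rule is easy to write.

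**Conclusion.** The point holds in a limited form. Applied literally, the two sections leave out of LCRIS a same-day reaction that is mild at first and moderate or worse from a later day, apart from the limb (B) and later-injection-day exceptions. They also grade a reaction that goes from moderate to severe as moderate at most under limb (A). The any-LCRIS count, the severe count and the percentage of injections can be too low; the moderate count can be too low or too high.

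This assumes that sites record severity changes as SAP 4.10.2 describes and that records are not joined for LCRIS. The size is unknown and probably small: related Phase 1 TEAEs were all mild, with the nine injection-site events coming from one subject (Protocol 2.3.4). No efficacy result or step of the testing sequence is touched. It is a change to consider, not a condition for relying on the safety report.

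**What to change.** In SAP 4.10.3.1, derive LCRIS per reaction:

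- Link records of the same preferred term and injection where one starts on the stop date of the one before.
- Take onset from the first record, end from the last, and severity as the maximum.
- For limb (A), require onset on the injection day and at least 2 days at moderate or worse, or ongoing at moderate or worse. Leave limb (B) unchanged.
- State whether 2 days means stop minus start or inclusive days.
- Use the same derivation for A in the (A/B) percentage.

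The cost is one paragraph and a derivation from AE records already collected. If the database is locked, SAP Section 1 provides for an addendum or documentation in the study report. The downside is that the any-LCRIS count may rise and be less comparable with the zero counts from Phases 1 and 2, if those were derived per record; a footnote with the per-record count preserves the comparison. Requiring 2 days at moderate or worse is a choice. Total duration with worst severity is an alternative, and would also count a reaction that is mild for two days and moderate for one.
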